7.7 Data Monitoring Committee

A DMC will be established for this trial. The DMC will include 3 physicians, including 1 hepatologist. Up and until safety data from the last patient in the Double-Blind Treatment Period have been reviewed, the DMC will conduct periodic reviews of safety data and will continuously review all ADRs with CTCAE grade 3 and all AEs with CTCAE grades 4 or 5. The DMC will recommend actions to the Sponsor, as appropriate. The DMC will be informed to what extent the data and analyses provided to them have been quality controlled. Members of the DMC will not be involved in other trial-related tasks.

The DMC will be decommissioned after the safety data from the Double-Blind Treatment Period have been reviewed. The Sponsor will then be responsible for the continued safety monitoring during the remainder of the Open-Label Extension Period.

The DMC procedures are described in the DMC Charter.

8 STATISTICAL CONSIDERATIONS

8.1 Statistical and Analytical Plans

Complete details of the statistical analyses to be performed will be documented in a SAP, which will be completed prior to database lock for the primary endpoint analysis. This document will include more details of the analysis populations, summary strategies, and any amendments to the below proposed analyses, if necessary. Any changes to the SAP will be outlined in the final clinical trial report. A separate analysis plan for the psychometric validation of the PLD-S and PLD-I will be submitted prior to database lock for the primary endpoint analysis.

8.2 Determination of Sample Size

In Hogan 2020, the comparison between pasireotide and placebo over 12 months resulted in a treatment difference in reducing htTLV of approximately 235 mL/m, or 9 to 10% expressed as percent change from baseline (50). The RSDs with the two analysis approaches were approximately 170 mL/m and 8%.

With 20 patients per treatment arm, the power is 80% if the true treatment difference is 165 mL/m (approximately 70% of the difference seen in the Hogan trial). This calculation is based on an assumed RSD of 180 mL/m using a t-test with a significance level of 5% (two-sided). With the same assumptions, the smallest observed treatment difference to give $p < 0.05$ is approximately 115 mL/m. If the 2 CAM2029 treatment arms are combined in the comparison to placebo, the number of patients in the comparison will be 40 versus 20. Assuming the same treatment difference, 165 mL/m, the power is approximately 90%. For a treatment difference of 141 mL/m, the power for the combined comparison would be approximately 80%.

With an assumed 15% drop-out rate the total number of patients required in the trial will be 69.

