6 SAMPLE SIZE DETERMINATION

The sample size calculation is based on a trial by Hogan et al comparing pasireotide to placebo (2). In this trial, the comparison between pasireotide and placebo over 12 months resulted in a treatment difference in reducing htTLV of approximately 235 mL/m, or 9-10% expressed as percent change from baseline. The residual SDs with the 2 analysis approaches were approximately 170 mL/m and 8%.

With 20 patients per treatment arm, the power is 80% if the true treatment difference is 165 mL/m (approximately 70% of the difference seen in the Hogan trial (2)). This calculation is based on an assumed residual SD of 180 mL/m using a t-test with a significance level of 5% (two-sided). With the same assumptions, the smallest observed treatment difference to give $p < 0.05$ is approximately 115 mL/m. If the two CAM2029 treatment arms are combined in the comparison to placebo, the number of patients in the comparison will be 40 vs 20. Assuming the same treatment difference, 165 mL/m, the power is approximately 90%. For a treatment difference of 141 mL/min, the power for the combined comparison would be approximately 80%.

With an assumed 15% drop-out rate the total number of patients required in the trial was estimated to be 69.

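### At the stated 15% drop-out, 69 patients leave about 19.5 per arm rather than the 20 behind every stated power; the effect is about one power point or less

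*Protocol*

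**What the plan says.** Protocol section 8.2 starts from the size needed after losses: "With 20 patients per treatment arm, the power is 80% if the true treatment difference is 165 mL/m". The residual standard deviation is 180 mL/m and the test is a two-sided 5% t-test. For the two doses together against placebo, "the number of patients in the comparison will be 40 versus 20", with power of approximately 90% at 165 mL/m and approximately 80% at 141 mL/m. The section then allows for losses: "With an assumed 15% drop-out rate the total number of patients required in the trial will be 69".

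SAP section 6 gives the same inputs and powers and closes with: "With an assumed 15% drop-out rate the total number of patients required in the trial was estimated to be 69".

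Neither document shows the formula that leads from 20 per arm to 69. Allocation is 1:1:1 (Protocol section 4.1), so 69 means 23 per arm. Protocol section 6.10.2 rules out replacing patients who withdraw.

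**The concern.** An allowance for drop-out should leave the number used in the power calculation once the assumed share has been lost. Here that number is 20 per arm, 60 in all, and the assumed loss is 15%. If 69 does not leave 60, then the total, the drop-out rate and the stated powers cannot all hold together.

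Two of the stated powers sit at 80%, the conventional threshold, so even a small shortfall could take them below it. With no replacement of withdrawals, nothing in the plan makes up the difference. What is at stake is whether the sample size justification is accurate in the two governing documents, and in a trial report that may repeat it. The trial's design and analysis are not affected.

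**Working it through.** **Inputs** (Protocol section 8.2, repeated in SAP section 6): 20 per arm; difference 165 mL/m, or 141 mL/m for the second combined calculation; standard deviation 180 mL/m; two-sided 5% t-test; drop-out 15%; total 69.

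**Step 1. Reproduce the stated powers at 20 per arm.** Power comes from the noncentral t distribution with n1 + n2 − 2 degrees of freedom and noncentrality δ / (180 × √(1/n1 + 1/n2)).

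- One dose, 20 v 20, 165 mL/m: 165 / (180 × √0.1) = 2.90 on 38 df. Power 80.6% (stated 80%).
- Combined, 40 v 20, 165 mL/m: 165 / (180 × √0.075) = 3.35 on 58 df. Power 90.8% (stated approximately 90%).
- Combined, 40 v 20, 141 mL/m: 141 / (180 × √0.075) = 2.86 on 58 df. Power 80.3% (stated approximately 80%).
- Smallest significant difference, 20 v 20: 2.024 × 180 × √0.1 = 115.2 mL/m (stated approximately 115).

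All four agree, so the inputs have been read as the plan intends.

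**Step 2. Check the total.**

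- Required to keep 60 after 15% loss: 60 / 0.85 = 70.6, so 71.
- Per arm: 20 / 0.85 = 23.5, so 24 per arm and 72 in total under 1:1:1.
- What 69 leaves: 69 × 0.85 = 58.65, or 58.65 / 3 = 19.55 per arm. The expected shortfall is 60 − 58.65 = 1.35 patients in the whole trial.
- Largest drop-out at which 69 still leaves 60: 1 − 60/69 = 13.0%.
- Possible origin of 69: 60 × 1.15 = 69.0 exactly. This suggests that the allowance was multiplied on rather than divided out.

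**Step 3. Power at the stated drop-out.** Same formula with 19.55 per arm (39.1 v 19.55 for the combined comparison), treating drop-outs as contributing no data.

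| Comparison | 20 per arm | 19.55 per arm | Change (points) |
|---|---|---|---|
| One dose, 165 mL/m | 80.6% | 79.7% | −0.9 |
| Combined, 165 mL/m | 90.8% | 90.2% | −0.6 |
| Combined, 141 mL/m | 80.3% | 79.4% | −0.9 |

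**Step 4. The same check under the planned model.** The primary analysis (Protocol section 8.9.2, SAP section 5.9.2.2) is one ANCOVA on all three arms with baseline as covariate. A single-dose contrast therefore draws on the residual degrees of freedom of the whole trial: 58.65 − 4 ≈ 55, against 37 for the two-arm t-test. At 19.55 per arm this gives 80.4% for one dose at 165 mL/m and 79.3% for the combined doses at 141 mL/m.

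**The case against.** The strongest reply is that the effect lies within the documents' own rounding. Two of the three powers are given as approximate; 79.7% and 90.2% round to the stated 80% and 90%, and 79.4% is fairly called approximately 80%. Elsewhere the total itself is approximate (Protocol sections 4.1 and 5.1, SAP section 2.2). This stands as regards consequence. It does not repair the sentence: the sample size sections present 69 as the number required, and a required number is rounded up from 70.6, not down.

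A second reply is that drop-outs are not a total loss. Patients who stop treatment are followed to Week 53 (Protocol section 6.10.1), and their data are used unless another somatostatin receptor ligand or a liver-reducing intervention has begun. All randomised patients are analysed, and missing Week 53 volumes are imputed from baseline, Week 13 and Week 25 (SAP section 5.3.1). Section 8.2 does not define drop-out. The powers in Step 3 are therefore on the conservative side. This also stands, but section 8.2 chose to allow for drop-out by inflating from 20 per arm, and its own inflation does not return 20.

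A reader might be tempted by four stronger inferences, which the documents do not support:

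- *The trial is materially underpowered.* It is not; the loss is at most about one point.
- *The 80% figures have no slack.* At 20 per arm they are 80.6% and 80.3%, so there is a little.
- *Only 19 per arm would remain.* That is 57 of 69, a 17.4% loss, not 15%.
- *The sponsor is shown to have multiplied by 1.15.* The match is exact, but no formula is given, so this is inference.

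**Conclusion.** The point holds as a minor error, present in both documents. The total of 69 does not deliver 20 per arm at 15% drop-out. It delivers an expected 19.55, and it covers drop-out of up to 13%. This follows from the plan's own figures and does not depend on how 69 was obtained.

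Under the stated t-test, and counting drop-outs as contributing nothing, the two powers given as 80% become 79.7% and 79.4%, and the 90% figure stays at 90.2%. It would go too far to say that both 80% figures fall below 80% in the analysis as planned: under the three-arm ANCOVA the single-dose power stays at 80.4%, and only the combined calculation at 141 mL/m dips, to 79.3%. The stated powers remain approximately right. These results take the standard deviation of 180 mL/m as given and the losses as equal across arms.

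**What to change.** Do not enrol more patients, and leave the 15% planning assumption on record rather than replacing it after the fact with 13%. Add one clarifying sentence to Protocol section 8.2 and to SAP section 6, for example: *With 69 randomised patients, about 19.5 per arm remain at 15% drop-out (20 per arm at up to 13%); if drop-outs contribute no data, power is then about 79.7% for one dose at 165 mL/m, 90.2% for the combined doses at 165 mL/m and 79.4% for the combined doses at 141 mL/m.*

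The cost is one sentence in each document and figures that are very slightly less favourable. SAP section 2 allows changes until database lock and unblinding for the primary analysis. Nothing changes in the design, the analysis, the significance level or the conduct of the trial.

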8.3 General Considerations

Categorical variables will be summarized using numbers and percentages of patients in each category, where the denominator for calculation is the underlying analysis set unless otherwise stated.

Continuous variables will be summarized with descriptive statistics, including number of available observations, mean, standard deviation, median, minimum and maximum, and quartiles where more appropriate.

For all efficacy endpoints, descriptive measures and 95% CIs for the difference in change from baseline between the treatment groups will be presented, unless otherwise specified.

Safety parameters will be presented descriptively.

The statistical analyses will be performed using version 9.4 or later of the SAS® statistical software package.

8.4 Patient Disposition

All patients screened and enrolled will be accounted for. All post-enrollment withdrawals will be summarized by reason for withdrawal from the trial. Patients who are screened but not enrolled will be listed.

8.5 Protocol Deviations

Major protocol deviation criteria will be established prior to each database lock.

8.6 Analysis Sets

8.6.1 Intention-to-Treat Analysis Set

The ITT analysis set will consist of all patients who were randomized to a treatment arm. Analyses based on this population will group patients according to the treatment they were randomized to receive, regardless of actual treatment received.

The efficacy analyses will be based on the ITT analysis set.

8.6.2 Full Analysis Set

The full analysis set comprises all patients in the ITT analysis set who were administered at least 1 dose of the IMP.

8.6.3 Per Protocol Analysis Set

The per protocol analysis set is defined as all patients in the ITT analysis set with no major protocol deviations that would have an impact on the efficacy assessment. Detailed criteria defining this analysis set will be documented in the SAP.

8.6.4 Pharmacokinetic Analysis Set

The PK analysis set comprises all patients who were administered at least 1 dose of CAM2029 and for whom at least 1 post-dose plasma octreotide concentration result is available.

The PK analysis set will be used for the analyses of PK data.

8.6.5 Safety Analysis Set

The safety analysis set comprises all patients who were administered at least one dose of IMP. Analyses based on this population will group patients according to the actual treatment the patients received.

The safety analyses will be based on the safety analysis set.

8.7 Trial Population

8.7.1 Demographics and other Baseline Characteristics

Descriptive statistics of demographics and other baseline characteristics will be presented by treatment arm and overall. All relevant demographic and baseline characteristics will be summarized using descriptive statistics.

8.7.2 Medical History

Medical history (recorded at screening) will be coded using the MedDRA and data will be listed and presented descriptively. Disease characteristics will also be listed and presented descriptively.

8.8 Prior and Concomitant Medications and Treatments

Prior and concomitant medications will be summarized by ATC classification second level (alphabetically), and the ATC classification fourth level (in decreasing order of frequency).

Prior and current medications or treatments of PLD or its related symptoms, including prophylactic treatment, will be listed, and summarized descriptively.

8.9 Efficacy Endpoints and Analyses

8.9.1 Missing Values

Procedural attempts with the aim to avoid missing data and keep the frequency of missing data to a minimum will be implemented in the trial.

Sensitivity analyses evaluating the impact of missing data will be performed and further described in the SAP.

8.9.2 Primary Efficacy Endpoint

The primary efficacy endpoint is change from baseline to Week 53 in htTLV as determined by MRI volumetry. In the analysis of the primary efficacy endpoint, the primary comparison will be between the average effect of the 2 CAM2029 doses compared to placebo. In addition, the 2 doses of CAM2029 will be compared with placebo separately, see [Section 8.10](#).

The primary efficacy endpoint will be analyzed using an ANCOVA model with fixed factor for treatment and baseline htTLV as covariate, within the framework of a multiple imputation method. Point estimates and the associated two-sided CI with 95% confidence level will be calculated for the difference in change. The absolute change analysis will be the primary analysis. In this ANCOVA model the average of the treatment effect of the 2 doses of CAM2029 (10 mg once weekly and 10 mg every 2 weeks) will be compared to placebo, i.e., the contrast for the treatment difference is $(0.5 \ 0.5 \ 0) - (0 \ 0 \ 1)$ where the 2 CAM2029 doses are given by the 2 first terms and placebo by the last. Additionally, each of the doses of CAM2029 will be compared with placebo separately, as described in the SAP.

The primary endpoint analysis will be performed when the last patient has completed the Double-Blind Treatment Period (Week 53).

The items that define the primary estimand are the following:

1. Treatment condition: The primary treatment condition of interest is the average effect of the CAM2029 treatment (10 mg once weekly and 10 mg every 2 weeks) vs placebo treatment. Thereafter, the treatment conditions of interest are the effects of:
 - CAM2029 10 mg once weekly vs placebo
 - CAM2029 10 mg every 2 weeks vs placebo
2. Target population: Patients in the ITT analysis set as defined by the inclusion/exclusion criteria in the trial.
3. Variable (endpoint): The variable addressing the primary clinical question is change from baseline in htTLV as assessed at Week 53.
4. Handling of intercurrent events: Intercurrent events will be handled through a combination of a treatment policy strategy and a hypothetical strategy depending on other treatment received and therapeutic interventions conducted while still in the trial:
 - IMP treatment discontinuation: Patients who discontinue treatment with IMP and do not receive another SRL or have any therapeutic interventions with the intention to reduce the liver size while still in the trial, will be analyzed according to a treatment policy strategy, i.e., observations collected after IMP discontinuation will be included in the analysis as they are collected.

- For patients who discontinue treatment with IMP and start receiving another SRL or have any therapeutic intervention with the intention to reduce the liver size while still in the trial, only observations collected prior to the start of the SRL will be included in the analyses. Observations collected after the start of the SRL and the therapeutic intervention will be handled using the method described below:
 - Use of another SRL: Patients who receive an SRL other than the trial IMP while still in the trial, will be handled according to a hypothetical strategy. I.e., any measurements of htTLV following start of any other SRL administration will be set to missing and not be used in the analysis. This hypothetical strategy is motivated by the fact that no approved alternative SRL treatment for PLD is available in most countries.
 - Therapeutic interventions: Patients undergoing therapeutic intervention with the intention to reduce the liver size while still in the trial will be handled according to a hypothetical strategy. I.e., measurements of htTLV following this intercurrent event will be set to missing and not used in the analysis. This strategy is motivated by the fact that such interventions may directly impact the primary endpoint without being related to the effect of the IMP.
 - Missing values: If the htTLV cannot be determined at Week 53, either due to start of another SRL treatment or after a therapeutic intervention with the intention to reduce the liver size after IMP discontinuation or values are missing for other reasons, missing values will be imputed using the multiple imputation method described in the SAP.
- d) Population level summary for comparison between treatment conditions: Mean change from baseline to Week 53 in htTLV.

The proposed *primary estimand* is the entity defined to address the effect of treatment with CAM2029 in reducing the progression in htTLV in PLD patients without any alternative treatment being available and with a diagnosis as defined by the inclusion and exclusion criteria.

Missing values

If the status of the htTLV cannot be determined at Week 53, either due to start of another SRL treatment and/or a therapeutic intervention with the intention to reduce the liver size after IMP discontinuation, or if values are missing for other reasons, then the missing values will be imputed using the multiple imputation method described in the SAP. Missing htTLV data at Week 53 will be imputed using multiple imputation assuming that data are missing at random within the groups used for imputation..

The imputation will be done within treatment arms defined by the randomized treatment. For these continuous endpoints, [REDACTED]. Results from the ANCOVA model with fixed factors for treatment and baseline as covariate on each imputed data set, will be combined using Rubin's rule (51).

8.9.2.1 Sensitivity Analyses

The following sensitivity analyses will be performed on the primary endpoint:

[figure not shown]
- Last observation carried forward analyzed in an ANCOVA with fixed factors for treatment and the baseline value as covariate, i.e., missing data will be imputed using last observed values post-baseline.
- A mixed model repeated measures model will be used to estimate the change from baseline.

- The primary endpoint will be analyzed using the same ANCOVA model with fixed factor for treatment and baseline htTLV as a covariate based on observed cases without imputation or handling of intercurrent events.
- If a significant difference can be detected from the primary analysis, a tipping point multiple imputation analysis as described in Ratitch et al. (2013) will be applied (52). A tipping point analysis is a means of exploring the influence of missingness on the overall conclusion by investigating a broad range regarding the missingness mechanism (from less conservative to more conservative, i.e., it will include scenarios where dropouts on CAM2029 have worse outcomes than dropouts on placebo). The analysis finds a (tipping) point in this range, at which conclusions of effect vary from being favorable to the treatment with CAM2029 to being unfavorable. Based on such a tipping point, clinical judgment can be applied as to the plausibility of the assumptions underlying this tipping point.

Sensitivity analyses will be described in detail in the SAP.

8.9.2.2 Supplementary Analyses

The following supplementary analyses will be performed on the primary endpoint:

Supplementary analyses will be described in detail in the SAP.

8.9.3 Secondary Efficacy Endpoints

8.9.3.1 Key Secondary Efficacy Endpoint

The key secondary efficacy endpoint is change from baseline to Week 53 in the PLD-S measure score and this endpoint will be analyzed with the same methods as for the primary endpoint. In the analysis of the key secondary efficacy endpoint, the main comparison will be between the average effect of the 2 CAM2029 doses compared to placebo. In addition, the 2 doses of CAM2029 will be compared with placebo separately, see also [Section 8.10](#).

8.9.3.2 Other Secondary Efficacy Endpoints

For the secondary efficacy endpoints listed below, the analyses will be described in detail in the SAP:

- Change from baseline in htTLV as determined by MRI volumetry
- Change from baseline in PLD-S measure score
- Change from baseline in height-adjusted total kidney volume as measured by MRI volumetry
- Change from baseline in total liver cyst volume determined by MRI volumetry
- Change from baseline in eGFR, assessed by the CKD-EPI cystatin C equation using serum concentrations of creatinine and cystatin C
- Change from baseline in PLD-I measure score
- Change from baseline in CGI-S score
- Change from baseline in PGI-S score
- PGI-C score by visit
- Change from baseline in SF-36 score
- Change from baseline in PLD-Q score

Point estimates and the associated 95% CI will be calculated for the difference in change at all time points. In the analysis of the secondary efficacy endpoints, the main comparison will be between the average effect of the 2 CAM2029 doses compared to placebo. In addition, the 2 doses of CAM2029 will be compared with placebo separately.

8.10 Adjustments for Multiplicity

Two doses of CAM2029 are analyzed in the trial. In order to protect the overall significance level, the following closed order testing procedure will be used:

1. The effect of the combined CAM2029 treatment groups compared to placebo on change in htTLV at Week 53
2. The effect of treatment with CAM2029 10 mg weekly compared to placebo on change in htTLV at Week 53
3. The effect of treatment with CAM2029 10 mg every 2 weeks compared to placebo on change in htTLV at Week 53

Each test will be performed on the 5% significance level starting with the first test in the list and stopping the testing procedure at the first test for which the p-value is larger than 0.05.

